Domain	Scale/measure	T ₂	T ₋₁	T ₁	T ₂	T ₃	T ₄	T ₅
		1W preop	1W postop	4 Mo	6 Mo	8 Mo	12 Mo	18 Mo
Pain-related functioning (primary outcome)	Pain Disability Index	x	x	x	x	x	x	x
Pain symptoms and characteristics	Pain intensity (VAS)	x	x	x	x	x	x	x
	Brief Pain Inventory (BPI)	x	x	x	x	x	x	x
	Neuropathic Pain Questionnaire (DN4)	x	x	x	x	x	x	x
	Central Sensitisation Questionnaire (CSI)	x	x	x	x	x	x	x
	Pain sensitivity testing	x	x	x	x	x	x	x
Physical functioning	General physical activity level (accelerometry)		x	x			x	x
	Upper limb performance (accelerometry)		x	x			x	x
	Upper limb function (DASH)	x	x	x	x	x	x	x
Emotional functioning	Pain Catastrophizing Scale (PCS)	x	x	x	x	x	x	x
	Depression, Anxiety and Stress Scale (DASS-21)	x	x	x	x	x	x	x
	Health-related quality of life (McGill Quality of life questionnaire)	x	x	x	x	x	x	x
Social functioning	Return to work rate			x	x	x	x	x
	QuickScan			x	x	x	x	x
	Return-to-work self-efficacy (RTWSE-19)			x	x	x	x	x

Table 3. Outcome measures of the EduCan Trial

Outcome	Assessment method
PAIN-RELATED FUNCTIONING (primary outcome)	
Pain-related functioning	Pain Disability Index (PDI). The PDI is a short, self-reported questionnaire for measuring the degree of interference of pain with normal role functioning (family/home responsibilities, recreation, social activity, occupation, sexual behavior, self-care, and life-support activity).(37, 38)
PAIN SYMPTOMS AND CHARACTERISTICS	
Pain intensity	Visual Analogue Scale (VAS). Present pain intensity and mean pain intensity during the past week for pain at the upper limb region (i.e. shoulder-neck region, arm, axilla, trunk side and breast region)
Brief Pain Inventory	Medication use, pain quality, pain location, pain severity and response to treatment.(39)
Presence of neuropathic pain	Douleur Neuropathique en 4 questions (DN4). The DN4 a questionnaire generating reliable and valid data for identifying pain of predominantly neuropathic origin.(40)
Presence of hypersensitivity of the central nervous system	Central Sensitisation Inventory (SCI). The SCI is a questionnaire generating reliable and valid data to assess symptoms related to central sensitization mechanisms.(41)
Pain sensitivity testing	
- Quantitative Sensory testing: Mechanical detection and pain thresholds*
 
Twelve monofilaments (MARSTOCK nerve test - Optihair2, Schriesheim, Germany) with a force from 0.25 to 512 mN are used. The mechanical detection threshold is defined as the lowest mechanical force that the participant can detect. The mechanical pain threshold is defined as the lowest mechanical force that the participant perceives as painful or unpleasant. Monofilaments are applied with a rate of 2 seconds 'on' and 2 seconds 'off' at the inner side of the upper arm and lateral trunk side.
 
- Quantitative Sensory testing: Temperature detection and pain thresholds*
 
The computerized thermotest device TSA-II-NeuroSensory Analyser is used. The method of limits is used. The detection and pain thresholds are measured as the first identified stimulus under increasing stimulus intensities. The participant has to push the button once the stimulus is detected or perceived as painful or unpleasant. This is repeated three times for each threshold. The mean of three stimuli for each threshold is calculated and used for analysis.(42).
 
- Quantitative Sensory testing: Pressure Pain Thresholds*
 
Measured by a digital Wagner FPX™ algometer. Points of measurement are defined by palpation for most tender muscle points (one per muscle) at the major pectoral muscle region, the lateral trunk side and upper trapezius muscle region. The participant is asked to say 'stop' when the sensation of pressure first changes to pain. The mean value of the 2 measurements is calculated and used for analysis.(43)
 
- Presence of widespread pain/secondary hyperalgesia
 
Quantitative Sensory Testing is performed both at the local painful area as at remote body parts (i.e. quadriceps muscle at the non-affected side) and pain distribution is displayed on a body diagram
 
- Presence and degree of impaired nociceptive inhibitory
 
Assessment of conditioned pain modulation will be done using the Medoc two thermode Q-Sense CPM system. This system involves a 'test' stimulus and a 'conditioning' stimulus applied on the ulnar

mechanisms (i.e. conditioned pain modulation)	side of the forearms. The test stimulus (at the affected side) is used to assess pain sensitivity to a warmth stimulus pre- and post the noxious conditioning stimulus and the difference is calculated between pre- and post-measures. When the second pressure pain threshold (i.e. test stimulus) is similar or lower than the first, dysfunctional inhibitory pain mechanisms are present.(44, 45)
- Presence and degree of enhanced facilitation mechanisms (i.e. wind-up)	Wind-up of pain or temporal summation will be assessed by applying repetitive nociceptive stimulation with a 26g Nylon monofilament at the major pectoral muscle at the affected side. The perceived intensity of the stimulus (the first, the last and aftersensations) are reported by using a Numeric Rating Scale. The temporal summation value is calculated as the difference between the first and the last stimuli or the slope of the increase in pain intensity. A response for enhanced temporal summation is deemed positive if participants perceive the initial stimulus as non-noxious, but it becomes noxious, increasing by at least two-points on a Numeric Rating Scale, or if baseline pain intensity increases by at least two points.(44-46)
- Presence and degree of hypersensitivity to non-mechanical stimuli	The Central Sensitization Inventory, a questionnaire generating reliable and valid data to assess symptoms related to central sensitization mechanisms (47-49)
PHYSICAL FUNCTIONING	
General physical activity and upper limb performance	Three ActiLife accelerometers, one on the pelvis (7 consecutive days) and one on each wrist (3 consecutive days), will be worn during waking hours. Outcome parameters are general activity level, unimanual/bimanual time and intensity of both unimanual/bimanual use. The ActiLife v6.9.5 Firmware v2.2.1 will be used to save raw data. Data will be further processed with Matlab®, using custom-written routines.(50, 51)
Upper limb function	DASH questionnaire. The DASH is a self-reported questionnaire on upper limb function.(3)
EMOTIONAL FUNCTIONING	
Pain catastrophizing	Pain Catastrophizing scale (PCS). The PCS is a self-reported questionnaire measuring catastrophic thinking related to pain. (53)
Depression, anxiety and stress	Depression Anxiety Stress scales 21 (DASS-21). The DASS-21 is a self-reported questionnaire that measures the three related states of depression, anxiety and stress. (54)

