Therapists and assessors are blinded to the allocation of the treatment groups. The therapists providing the standard physical therapy program will be unaware of the type of education received by the patient (PNE in the intervention group and biomedically-focused education in the control group). Assessors are blinded to the maximal extent possible. With regard to this, patients are asked not to communicate with the assessors about the intervention

received. Patients are masked for the allocation to the intervention/control group; they do not know which one is the experimental intervention and which one is the control intervention, however they will of course be aware of the intervention received.

At the end of the trial, the success of assessor blinding will be examined by asking whether the assessor thought the participant had received the experimental or control intervention, including the percentage of certainty (i.e. 50% certainty means a pure guess). The same will be done for patient masking. The research members performing statistical analysis will be blinded as well.

The randomization is computer-generated and is performed by using permuted blocks (size=4). An independent co-worker at the department carries out the randomization to ensure blinding of the research team. The sequence of randomization is determined by the patient's identification number, which she receives after signing informed consent. Participants are randomized in a 1:1 ratio between intervention and control arms.

Interventions

Standard physical therapy program

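### Does Table 3 classify conditioned pain modulation by a pressure threshold when the test it describes is thermal?

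*Combined protocol and SAP*

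**What the plan says.** The point sits in Table 3 (Outcomes), in the row on conditioned pain modulation, one of several tests grouped under pain sensitivity.

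- **Device:** "Assessment of conditioned pain modulation will be done using the Medoc two thermode Q-Sense CPM system".
- **Stimulus:** the test stimulus "is used to assess pain sensitivity to a warmth stimulus pre- and post the noxious conditioning stimulus".
- **Continuous measure:** "the difference is calculated between pre- and post-measures".
- **Classification rule:** "When the second pressure pain threshold (i.e. test stimulus) is similar or lower than the first, dysfunctional inhibitory pain mechanisms are present".

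Three other parts of the protocol bear on it. Pressure pain thresholds have their own entry in Table 3, measured with a digital algometer at the pectoral, lateral trunk and upper trapezius regions. Temperature thresholds also have their own entry, on another instrument: "The computerized thermotest device TSA-II-NeuroSensory Analyser is used". The neighbouring wind-up row gives a numeric criterion, "increasing by at least two-points on a Numeric Rating Scale". Table 2 schedules the whole group on one line, "Pain sensitivity testing", at all seven assessments.

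The Data analysis section models continuous secondary outcomes in a similar way to the primary outcome and assigns categorical data to logistic models. It does not name a class for conditioned pain modulation. On blinding, the Allocation and randomization section states: "The research members performing statistical analysis will be blinded as well".

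**The concern.** Two adjacent sentences describe the test stimulus in incompatible ways, first as warmth and then as a pressure threshold. Read literally, the rule needs a pressure threshold before and after conditioning. The row describes none, and the separate pressure item lists neither the forearm site nor a conditioning stimulus.

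Correcting the word still leaves some points unstated:

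- The row gives no unit and no procedure for recording the response to warmth. If the response were a pain rating instead of a threshold, the stated direction would label working inhibition as dysfunction.
- The difference between the two measures has no stated order of subtraction.
- *Similar* has no margin, although the wind-up rule next to it has one.

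At stake would be the labelling of impaired pain inhibition in one secondary sub-test, and the sign attached to its continuous effect.

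**Working it through.** The documents give no figure for conditioned pain modulation, so there is nothing to reproduce. The check is a reading of the text followed by a small illustration.

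**1. Which word conflicts with the rest of the row?**

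| Element of the rule | What the row says elsewhere | Conflict? |
|---|---|---|
| pressure | two thermodes; warmth stimulus | yes |
| pain threshold | pain sensitivity to that stimulus | no |
| the gloss naming the test stimulus | the test stimulus is warmth | no; it identifies the intended response |
| similar or lower means dysfunctional | a pre/post difference is taken | no, if the response is a threshold |

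Only one word conflicts. Without it, the rule compares a second pain threshold with a first.

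**2. Is the direction coherent?** The values here are invented for illustration; the rule is dysfunctional if second ≤ first.

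- Threshold rising from 44.0 to 45.5 (inhibition present): functional, correct.
- Threshold falling from 44.0 to 43.5 (inhibition absent): dysfunctional, correct.
- Rating falling from 60 to 45 (inhibition present): dysfunctional, reversed.
- Rating rising from 60 to 68 (inhibition absent): functional, reversed.

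The direction fails only for a rating. The row mentions no rating, whereas the wind-up row names its rating scale.

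**3. Does the order of subtraction matter?** For the first threshold example, post minus pre is 45.5 − 44.0 = +1.5 and pre minus post is −1.5. Reversing the order changes the sign of every estimate and swaps the ends of its interval. It leaves the interval width and the p-value unchanged. On the threshold reading, the rule already shows which direction means impairment.

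**4. Does the margin for *similar* matter?** Assume that the post-minus-pre threshold difference, in SD units, is normal with mean μ and SD 1, and that *similar or lower* means a difference of at most m. The share classed as dysfunctional is then Φ(m − μ). The values of μ and m, and normality, are assumptions.

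| μ | m = 0 | m = 0.25 | m = 0.5 | rise, 0 to 0.25 | rise, 0 to 0.5 |
|---|---|---|---|---|---|
| 0.2 | 0.421 | 0.520 | 0.618 | 9.9 points | 19.7 points |
| 0.5 | 0.309 | 0.401 | 0.500 | 9.3 points | 19.1 points |
| 0.8 | 0.212 | 0.291 | 0.382 | 7.9 points | 17.0 points |

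The between-arm odds ratio is [p₁/(1 − p₁)] / [p₂/(1 − p₂)], with the same m in both arms. For means 0.2 and 0.5 at m = 0 it is (0.421/0.579) / (0.309/0.691) = 1.63 from unrounded shares.

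| Arm means | m = 0 | m = 0.25 | m = 0.5 |
|---|---|---|---|
| 0.2 vs 0.5 | 1.628 | 1.616 | 1.617 |
| 0.5 vs 0.8 | 1.660 | 1.632 | 1.617 |

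The margin moves the prevalence in each arm and hardly moves the comparison between arms.

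**5. Scope.** At most 184 women × 7 assessments = 1,288 classifications before dropout. This is an upper bound: Table 2 schedules the group of tests and not each sub-test, and the Outcomes text says that not every parameter is taken at every visit.

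**The case for a change.** The strongest case for a change is that a protocol should define its own outcomes, and this row does not do so completely. The two sentences are both current text, and nothing suggests an extraction fault. The row is titled as presence and degree, so a yes/no class is evidently contemplated, and a logistic model for it would be natural. The unit and recording method are given only for the other thermal device. A rule that would invert if the response were a rating deserves to have its response named. The adjacent wind-up criterion shows that numeric cut-offs are the table's own standard, and the repair would take one sentence and no new measurements.

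Part of this stands. The word is wrong, the unit is missing and *similar* has no number. If the prevalence of impaired inhibition is reported, the margin used must be reported with it, because the illustration shows that prevalence depends on it.

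The rest is weaker. The rating reading has no support in the text: it requires setting aside *threshold*, which conflicts with nothing, and an analyst would also have to apply a threshold rule to a rating without noticing. The rule cites two published sources that may give the method or the margin. They were not available here, so neither side can rely on them.

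**Conclusion.** The inconsistency is a clerical slip, and the remaining silence is ordinary missing detail that analysts can fill sensibly. The rule's own gloss leads to the warmth response, the stated direction suits a threshold, and the order of subtraction is a reporting convention. A margin chosen by blinded analysts and applied equally to both arms leaves the expected treatment comparison almost where it was, with odds ratios of 1.62 to 1.66 in the cases examined.

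The reach is one secondary sub-test whose binary analysis the plan does not state. Neither the Pain Disability Index analysis at 12 months nor the sample size uses it.

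The conclusion rests on the threshold reading of the rule and, for the margin, on the assumed normal model. If the recorded response proved to be a rating, the direction would have to be read the other way. That would be a matter of correct scoring and not of trial design. No change to the plan follows.

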Statistical analysis will be intention-to-treat and will comply with the Consolidated Standards of Reporting Trials (CONSORT) guidelines. Analysis will be conducted in a blinded way. The continuous data will be summarized using mean, SD, median and range values. The primary outcome will be analyzed using multilevel linear regression models for repeated (longitudinal) measures, using an unstructured covariance matrix. The mean change from baseline (i.e. preoperative assessment) to 4, 6, 8, 12 and 18 months (with correction for the postoperative assessment), will be estimated using contrast statements for each of the treatment arms. The difference in mean changes and their 95% CIs between interventions will be plotted graphically so that change can be assessed over the course of the study. Continuous secondary outcomes will be assessed in a similar way to the primary outcome. Categorical data will be analyzed using logistic models. For non-repeated continuous and binary measurements, ordinary linear regression and logistic models will be used, respectively.

Data security and management

Participant data are stored on a secure database in accordance with the General Data Protection Regulations (2018). Data is de-identified and a unique trial identification number

used on all participant communication. Clinical and patient forms are being checked for completeness and congruity before data entry onto the database. Data will undergo additional checks to ensure consistency between data submitted and original paper forms. Trial documentation and data will be archived for at least 10 years after completion of the trial.

Trial monitoring

The steering committee of the research team will oversee all aspects of design, delivery, quality assurance and data analysis. The steering committee will monitor the trial at least once per year.

ETHICS AND DISSEMINATION

Ethical considerations

The EduCan Trial applies the principles established in the Declaration of Helsinki. Participants provide written informed consent before data collection. Only de-identified coded and interpreted data will be shared between the members of the research team. Ethics approval was granted by the local Ethical Committee of the University Hospitals Leuven (s60702).

Dissemination of results

